5.3.4 Day 7 visit

It is intended that the Day 7 interaction with the patient is made by a clinical professional who can assess whether the patient has recovered. Patients may be visited at home on Day 7 (to collect research bloods and [REDACTED] as well as receiving the daily video (phone) call. If at this visit/during the call, it is assessed that the patient (on the treatment arm) has recovered, the patient may be asked to discontinue with camostat administration, and the drug will be disposed of as per an approved process. Follow up calls and visits as per protocol will continue.

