Camostat has been in clinical use for over 30 years and is indicated for the treatment of acute symptoms of chronic pancreatitis (recommended dose 600 mg [200 mg tds]) and for the treatment of postoperative reflux oesophagitis (recommended dose 300 mg [100 mg tds]). Dosing instructions in the approved Package Insert state doses should be taken after a meal for the treatment of postoperative reflux oesophagitis but no guidance on dosing in a fed or fasted state is given for the treatment of chronic pancreatitis. The recent unpublished data from the Ono Pharmaceutical Co. Ltd. Phase I trial (NCT04451083) has [redacted] (see Section 5.2), [redacted]

[REDACTED]. It is likely that the safety data for the use of camostat in the treatment of chronic pancreatitis (total daily dose 600 mg [200 mg tds]) will have been generated from a mixed population in terms of dosing in both a fed and fasted state, but with no obvious difference in adverse event (AE) profile noted and a known, acceptable safety profile for the agent at the recommended dose and schedule.

Additional safety data to support the 200 mg qds dosing schedule in a fasted state is provided from the ongoing NCT04451083 trial. As noted above, two cohorts of healthy Japanese male adults (n=7 per cohort) were administered a single dose of camostat [REDACTED] on Day 1 and then [REDACTED]

[REDACTED] dose proposed in the CRUKD/20/002 trial [200 mg qds]). In this trial, [REDACTED]

[REDACTED] (Ono Pharmaceutical Co., Ltd., 2020). Pharmacokinetic parameters reported in this trial for doses administered fasted, [REDACTED]

[REDACTED] (refer to the current version of the 'Camostat Investigator's Brochure' for further details).

The camostat dose proposed for the treatment arm in the CRUKD/20/002 trial is therefore a total daily dose of 800 mg (200 mg qds) for 14 days. Whilst the proposed 14-day dosing period is double that explored in the ongoing NCT04451083 trial, the total daily dose to be administered is three-fold less and considered acceptable based on the safety data available and lack of accumulation observed. Patients will be required to take their doses one hour before each meal and then before bed, with an interval of approximately three hours between eating and the next dose, so approximately four hours apart (except for the overnight interval between the last dose on one day and first dose of the next day which will be longer) and at the same time each day.

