4 OBJECTIVES AND ENDPOINTS

Primary Objective and Endpoint	
Objective	Endpoint
To further assess the safety and toxicity profile of camostat, to support integration into a Phase III trial.	Causality and severity of each adverse event (AE) to camostat.
Secondary Objectives and Endpoints	
Objective	Endpoint
To confirm that the PK profile aligns with the established PK profile for the active metabolite of camostat, 4-(4-guanidinobenzoyloxy) phenyl acetic acid (GBPA).	Confirm PK parameters of GBPA as assessed by population estimates from population PK analysis (popPK).
To assess the ability of camostat to reduce the requirement for COVID-19 related hospital admission in community patients with SARS-CoV-2 infection.	Rate of COVID-19 related hospital admission in community patients with SARS-CoV-2 infection.
To evaluate the requirement for supplementary oxygen (non-invasive or mechanical invasive) in patients who have received camostat as treatment for SARS-CoV-2 infection.	Supplementary oxygen-free days at 28 days (from randomisation).
To evaluate the requirement for ventilation in patients who have received camostat as treatment for SARS-CoV-2 infection.	Ventilator-free days at 28 days (from randomisation).
To evaluate efficacy of camostat by effect on COVID-19 related clinical improvement.	
Time Frame: Days 1-28
 
Time to worst point on the scale or deterioration of two points or more (from randomisation) on a 9-point category ordinal scale.
 
9-point category ordinal scale:
 
 0. Uninfected, no clinical or virological evidence of infection 1. Ambulatory, no limitation of activities 2. Ambulatory, limitation of activities 3. Hospitalised – mild disease, no oxygen therapy 4. Hospitalised – mild disease, oxygen by mask or nasal prongs 5. Hospitalised – severe disease, non-invasive ventilation or high-flow oxygen 6. Hospitalised – severe disease, intubation and mechanical ventilation 7. Hospitalised – severe disease, ventilation and additional organ support – vasopressors, renal replacement therapy (RRT), extracorporeal membrane oxygenation (ECMO) 8. Death

Research Objectives and Endpoints	
Objective	Endpoint
[REDACTED]	[REDACTED] [REDACTED] [REDACTED]
[REDACTED]	[REDACTED] [REDACTED] [REDACTED] [REDACTED] [REDACTED]
[REDACTED]	[REDACTED] [REDACTED]

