5 TRIAL DESIGN

5.1 Summary of trial design

A randomised, multicentre, prospective, open label clinical trial.

The trial aims to recruit up to 100 patients.

The Trial Management Group (TMG) described in Section 5.2.1, will perform ongoing review of the emerging data to inform adaptive decision making during the trial. Please see Section 5.2.1. for further details.

During the trial, patient enrichment strategies may be implemented e.g. adapting the inclusion criteria to include emerging co-morbidities, neutrophil/lymphocyte ratio, other blood biomarkers, age, in order to support trial endpoints and feasibility. All clinical data will be reviewed on a regular basis by the Sponsor and TMG to inform this adaptive design, collaborating with the Trial Steering Committee (TSC) as per Section 5.2.2.

If review of the data (during any part of the trial) results in proposed substantial amendments, these will be submitted to the Medicines and Healthcare products Regulatory Agency (MHRA) and Research Ethics Committee (REC) for an opinion.

Patients may be identified in/through various settings e.g. GP practices, primary care COVID hubs, community-based testing centre, drive through testing facilities, advertisement, secondary care or equivalent clinical settings. Further detail on how patients will be recruited is provided in Section 9.1. It is likely that testing availability and strategy will change in the UK and the trial will respond by engaging with testing sites as applicable, to support recruitment. Before any new sites are opened for this trial, risk assessments will be performed to ensure that the protocol and procedures can be performed safely for both patients and site staff.

If a patient consents to the trial and fulfils eligibility criteria, they will be randomised to either the treatment arm or the control arm. Patients in the treatment arm will be asked to take camostat for 14 consecutive days and patients in the control arm will be asked to continue with best supportive care.

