Assessment ⁶	Testing site	Home (or at site if permitted)	Home visit	Daily video call (or phone)	Home visit (or at site if permitted)	Daily call	Home visit (or at site if permitted)	Video call (or phone)	Video call (or phone)
Blood (FBC& U&Es & other markers)							■		
Blood - PK		X							
Pregnancy test for women of childbearing potential									
Demographics		X							
▪ Height, weight									
▪ Medical history									
▪ Risk factors									
▪ COVID-19 symptoms check									
▪ COVID-age risk									
Delivery of camostat ^c				X					
Camostat administration ^E				X					
				X					
				(first dose)					
					X				
					(if patient recovered, discontinue camostat)				
Documentation of supplementary oxygen administration/ high-flow oxygen device						X			
Assessment of:		X				X		X	
▪ ordinal scale status assessment									
Call with clinical researcher				X		X		X	X

A. The intention is that home visits, by a clinical professional, occur on Days 7 and 14 to take research bloods, PK bloods and repeat swab. However, this requirement may change if patients are permitted to provide samples by visiting the site. If the Sponsor and site decide that sampling is not required, this will be communicated to the patient. The Day 7 and 14 video (phone) calls will still go ahead as planned regardless of sampling.

■

C. If randomised to the camostat arm, patients will also receive camostat tablets to last for 14 days.

D. Two readings a day.

E. Trial packs and, for those patients randomised to the treatment arm, camostat may be delivered by courier or site staff.

■

G. For community patients, home visits can be performed on site if permitted by government guidance. **For hospital based patients these assessments may be performed face to face, if feasible.**

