7.4 Endpoints/outcome measures to be reported

Primary and secondary endpoints will be reported on the clinicaltrials.gov website as outcome measures as follows. All secondary endpoint data will be taken from Table 9 and PK data relating to the PK secondary endpoint will be taken from the PK final report.

Primary Objective and Endpoint		Endpoint	Outcome Measures
To further assess the safety and toxicity profile of camostat, to support integration into a Phase III trial.	Causality and severity of each adverse event (AE) to camostat.		
Measure Title: Number of camostat related AEs and SAEs.
 
Measure Description: Number of camostat related AEs and SAEs
 
Measure Title: Number of AEs by severity grade
 
Measure Description: Number of AEs by severity grade (mild, moderate, severe)
 
Information to be presented: Refer to programmed table "Primary endpoint reporting for clinicaltrials.gov"

			Time frame: Days 1-28
Secondary Objectives and Endpoints		Endpoint	
To confirm that the PK profile aligns with the established PK profile for the active metabolite of camostat, 4-(4-Guanidinobenzoyloxy)phenylacetic acid (GBPA).	Confirm PK parameters of GBPA as assessed by population estimates from population PK analysis (popPK).		
Measure Title: PK parameter Maximum concentration (Cmax) of 4-(4-Guanidinobenzoyloxy)phenylacetic acid (GBPA).
 
Measure Description: Maximum concentration (Cmax) of GBPA as assessed by population estimates from population PK analysis
 
Time frame: Days 7 and 14

Information to be presented: Mean and standard deviation for each arm at each time point for each arm (to be provided in final PK report).
	
Measure Title: PK parameter area under the curve (AUC) of GBPA

Measure Description: Area under the curve (AUC) of GBPA, as assessed by population estimates from population PK analysis
	
Time frame: Days 7 and 14
 
Information to be presented: Mean and standard deviation for each arm at each time point for each arm (to be provided in final PK report).

Measure Title: PK parameter time to maximum concentration (Tmax) of GBPA, as assessed by population estimates from population PK analysis
	
Measure Description: Time to maximum concentration (Tmax) of GBPA, as assessed by population estimates from population PK analysis

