11.1 Populations

The efficacy population will only include patients from the camostat arm where they have completed 5 days of treatment and in the control arm where they have completed 14 days of treatment or reached an endpoint (eg hospitalisation). All primary and secondary analyses will be conducted with this population. An intention-to-treat analysis of the main secondary outcomes (COVID-19 related hospital admissions, supplementary oxygen-free days, ventilator-free days, time to worst point on the 9-point ordinal scale) will also be conducted, should the data allow.

Patients who agree to the taking of blood samples will be included in the analysis of the PK data. The mean and SD will be reported at each time point (Days 7 and 14), as will the mean changes. The data may be log (or other) transformed if not normally distributed. [REDACTED]

[REDACTED] Change will be
change from previous blood test.

The safety population will include all patients with at least one dose of treatment (camostat or control). Safety data will be collected from the date of written consent. Safety variables will be summarised by descriptive statistics.

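### A patient judged recovered at Day 7 may stop camostat, yet the Day 14 PK summaries carry no still-on-drug condition and no safety table shows how many patients were dosed in the second week

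*Protocol*

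**What the plan says.** The SAP file is a reporting analysis plan (RAP, sections 2 to 9) with the statistical analysis plan appended (sections 10 to 13).

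**Regimen.** Protocol 5.1 states: "Patients in the treatment arm will be asked to take camostat for 14 consecutive days". Protocol 5.3.2 plans the same duration for the whole treatment arm. Protocol 5.3.4 then makes an exception: if a clinical professional judges at Day 7 that a treated patient has recovered, "the patient may be asked to discontinue with camostat administration, and the drug will be disposed of as per an approved process". The schedule of assessments (Table 1, end of section 8.5) puts it as an instruction: "if patient recovered, discontinue camostat". The text supplied gives no criterion for recovery. After a stop, "Follow up calls and visits as per protocol will continue", and PK blood is intended at the Day 14 visit.

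**PK.** SAP 11.1 states: "Patients who agree to the taking of blood samples will be included in the analysis of the PK data". It plans the mean and SD at Days 7 and 14 and the mean changes, with a log transformation if the data are not normal. The PK population in RAP 5.1 needs only one dose. RAP 7.4 reports Cmax, AUC and half-life at Days 7 and 14 as "Mean and standard deviation for each arm at each time point", and Tmax as median and range. None of these places requires the patient to be taking camostat when sampled.

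**Safety.** The primary objective is "To further assess the safety and toxicity profile of camostat, to support integration into a Phase III trial". It names no duration. Protocol 3.2 says of the supporting Phase I study: "Whilst the proposed 14-day dosing period is double that explored in the ongoing NCT04451083 trial". The adverse-event tables in RAP 6.7 count patients in the safety population by arm, with no split by onset week or by whether the patient was still dosing.

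**The concern.** The Day 7 stop depends on outcome. Patients who have recovered can leave treatment at that point, and Protocol 5.3.3 separately withdraws treatment when an event is judged related to camostat. Those who dose in Days 8-14 are therefore weighted towards patients who have not recovered and who have tolerated the drug so far.

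Two things are at stake. First, the PK objective is to confirm agreement with the known GBPA profile. If off-drug samples enter the Day 14 summaries, the Day 7 to Day 14 change partly measures who stopped. Second, Days 8-14 are where this trial goes beyond the duration of its supporting Phase I study. A Phase III planner who reads one arm-level incidence cannot tell how many patients that second-week evidence rests on.

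**Working it through.** **The plan's own figures.** The plan gives no precision figure for safety or PK. Its only one is for the recruitment rate (Protocol 13.2), and it reproduces: 100/0.50 = 200 approached, standard error √(0.25/200) = 3.5%. Nothing below depends on it.

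**Inputs.** Half-life 100 min (Protocol 3.2); visit windows Day 7 ± 1 and Day 14 − 2 (synopsis and Table 1); up to 50 patients per arm (synopsis, RAP section 4). The share r of camostat patients who stop at Day 7 is not in the documents. I take 20%, 40% and 60% as assumptions.

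**Step 1: drug left at the Day 14 sample.** The shortest gap is Day 8 to Day 12, 4 days; the nominal gap is 7 days; the longest is Day 6 to Day 14, 8 days. Half-lives elapsed = days × 1440/100, and the fraction left is 2 to the minus that number.

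| Days off drug | Half-lives | Fraction left |
|---|---|---|
| 4 | 57.6 | 4.6 × 10⁻¹⁸ |
| 7 | 100.8 | 4.5 × 10⁻³¹ |
| 8 | 115.2 | 2.1 × 10⁻³⁵ |

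Any such sample is effectively zero, and a zero cannot be log-transformed.

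**Step 2: effect on a Day 14 mean of concentrations.** If stoppers are sampled in the same proportion as the others, the mean is (1 − r) × the on-drug mean. With on-drug coefficient of variation c, the mixture has √[(1 − r)c² + r(1 − r)]/(1 − r). I assume c = 50%.

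| r | Mean, as % of on-drug mean | Coefficient of variation |
|---|---|---|
| 0 | 100% | 50% |
| 20% | 80% | 75% |
| 40% | 60% | 104% |
| 60% | 40% | 146% |

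**Step 3: what the second week can show.** Patients dosing after Day 7 number 50 × (1 − r), ignoring other withdrawals. If an event type is never seen in n patients, the exact two-sided 95% upper limit is 1 − 0.025^(1/n).

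| r | n | Upper limit |
|---|---|---|
| 0 | 50 | 7.1% |
| 20% | 40 | 8.8% |
| 40% | 30 | 11.6% |
| 60% | 20 | 16.8% |

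**The case against.** **On safety, much of the objection stands.** A reader might infer that the primary objective is the safety of a full 14-day course and that the adverse-event tables misstate it. The documents do not support that. The objective names no duration, and 14 days is a planned regimen to which section 5.3.4 states an exception. All treated patients stay in the safety population with events collected to Day 28, so whole-period incidence validly describes the regimen as used. No second-week rate is planned, so none is understated. A reader might also infer that only slow recoverers dose in week 2. That would follow from the schedule's wording, but section 5.3.4 makes the stop discretionary.

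The extent of stopping will also be visible. *Recovered* is a row in RAP Table 2 and in the registry participant flow (RAP 7.2), RAP 6.1 describes discontinuations by number of doses, and RAP Table 3 gives modification dates. RAP 6.6 leaves room for further safety analyses. None of these, however, links event onset to dosing status in a planned table. RAP 6.10 defines onset from first dose, but no listed table uses it.

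A still-dosing denominator has its own flaw. It is selected on non-recovery and tolerance after randomisation and has no control counterpart, so it cannot carry a comparison between arms.

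**On PK, part of the objection stands.** The endpoint is a population PK analysis, and the diary records dose times (Protocol 7.2.5). A model that uses them is not distorted in the way shown above, and a model-based half-life does not become zero off drug. SAP 11.1 does not say which quantity is averaged, and redacted text follows it. Sampling needs consent and may be waived, and the laboratory manual was not available. Still, the inclusion rule as written admits off-drug samples, and RAP 7.4 does not say what a Day 14 Cmax or AUC means for someone who stopped a week before.

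**Conclusion.** The point holds in a limited form. The regimen is worded in three ways (14 consecutive days, an optional stop, an instructed stop), and these must be reconciled; this review proposes no clinical rule.

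The clearest statistical gap is the missing on-drug condition in the simple Day 7 and Day 14 PK summaries. Each stopper sampled at Day 14 adds a near-zero value. A mean of concentrations falls by the stopping share, for example to 60% of the on-drug mean at an assumed 40%. This rests on concentrations being averaged and on stoppers giving Day 14 samples as often as the others. The population PK endpoint itself is not shown to be invalid.

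The safety gap is smaller and concerns interpretation. The plan does not show how many patients support a statement about Days 8-14. With no events of a given type, the upper limit moves from 7.1% for 50 patients to 8.8%, 11.6% or 16.8% for 40, 30 or 20. The true stopping share may lie outside the range shown.

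**What to change.** 1. Reconcile Protocol 5.1, 5.3.2, 5.3.4 and the schedule of assessments on the planned duration and the Day 7 stop, and describe the studied regimen in the clinical study report accordingly.
2. In SAP 11.1 and RAP 7.4, limit the Day 14 PK summaries and the Day 7 to Day 14 changes to camostat patients who, by dosing diary, were still dosing at the sample. State that the population PK analysis uses time since last dose.
3. In RAP 6.7, add adverse-event incidence by arm for onset in Days 1-7, 8-14 and 15-28. Keep the full safety population of each arm for the comparison between arms.
4. Beside that table, give the number in the camostat arm still dosing at Day 8 and at Day 14. Present it as descriptive context, with a note that the group is selected on non-recovery and tolerance. Any statement in the clinical study report on second-week tolerability should cite this number.

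The cost is reconciled wording, one extra table and a sentence or two on PK. Event onset dates (Protocol 12.3) and dose times (Protocol 7.2.5) are already collected. The downside is that the second-week statement will be less precise than a reader might now assume from 50 treated patients.

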5.3.5 Patient hospital admission during Days 1-14

If during Days 1-14 the patient is admitted to hospital due to COVID-19, patients on the treatment arm will be asked to continue to take their camostat as per protocol following agreement from the treating

clinician. A patient identification (ID) card will be provided to all patients with relevant contact details. Patients requiring hospital admission will continue to take camostat unless contraindicated by their clinical condition or other clinical care.

For patients who are hospitalised, clinical research teams should still seek to perform the protocol mandated assessments as per Section 8.3, so long as they do not interfere with clinical care and management of the patient.

5.3.6 Pharmacokinetic sampling

The Sponsor may propose that for patients who are hospitalised, if they have consented, and so long as the sampling schedule does not interfere with their hospital care, pharmacokinetic (PK) blood samples may be taken at Sponsor defined timepoints for analysis as per laboratory manual.

The patient will be asked to consent to this when first recruited to the trial and then asked again for verbal affirmation of consent (recorded in the patient's medical record) before these blood samples are taken. If the patient is unable to give consent or incapacitated, these samples will not be taken.

A maximum of 4 mL of blood will be taken at each timepoint for this analysis.

During the course of the trial, patients who remain able to recover at home, may also be asked to consent to PK sampling. Patients will be asked to consent to this at the time of recruitment and verbal affirmation of consent will be confirmed with the patient (and documented in the patient's medical record) before these samples are taken.

The process for PK sampling for this trial will be included in the laboratory manual. PK samples will be analysed to confirm that the PK profile aligns with the established PK profile for the active metabolite of camostat, 4-(4-guanidinobenzoyloxy) phenyl acetic acid (GBPA) and will be assessed by population estimates from population PK analysis (popPK).

5.3.7 Concomitant medications

Routinely used medications for the alleviation/treatment of symptoms of COVID-19 are permitted. Only approved anti-viral therapies to treat SARS-CoV-2 will be permitted.

Any other medication (including over the counter or prescription medicines, vitamins, and/or herbal supplements) that the patient is receiving at the time of enrolment (including screening) or receives during the study must be recorded in the eCRF along with:

- Reason for use.
- Dates of administration including start and end dates.
- Dosage information including dose and frequency.

The COVID-19 vaccine is currently not recommended for anyone who has had a positive test within 28 days or 28 days after symptoms started and not before symptoms have resolved. Please also refer to the current NHS guidelines for information.

